7.1.1 Adverse Events List(s)

7.1.1.1 Adverse Event List(s) for Tazarotene

Reported adverse events with tazarotene include pruritus, burning/stinging, erythema, worsening of psoriasis, irritation, skin pain, rash, desquamation, irritant contact dermatitis, skin inflammation, fissuring, bleeding and skin discoloration.

7.2 Adverse Event Characteristics

- All adverse events will be graded using CTCAE v 5.0. Cutaneous AEs due to topicals will also be characterized as in the dose modification table (section 6.0 and 7.3.4). Attribution of the AE:
 - Definite – The AE is *clearly related* to the study treatment.
 - Probable – The AE is *likely related* to the study treatment.
 - Possible – The AE *may be related* to the study treatment.
 - Unlikely – The AE is *doubtfully related* to the study treatment.
 - Unrelated – The AE is *clearly NOT related* to the study treatment.

7.3 Adverse Event Reporting

- 7.3.1 In the event of an unanticipated problem or life-threatening complications treating investigators must immediately notify the Overall PI.
- 7.3.2 Investigators **must** report to the Overall PI any adverse event (AE) that occurs after the initial dose of study treatment, during treatment, or within 28 days of the last dose of treatment on the local institutional SAE form.
- 7.3.3 DF/HCC Adverse Event Reporting Guidelines

Investigative sites within DF/HCC will report AEs directly to the DFCI Office for Human Research Studies (OHRS) per the DFCI IRB reporting policy.

- 7.3.4 Protocol-Specific Adverse Event Reporting Exclusions

For this protocol only, the AEs/grades listed below do not require expedited reporting to the Overall PI or the DFCI IRB. However, they still must be reported through the routine reporting mechanism (i.e. case report form).

- \leq Grade 1 (mild irritation or peeling without pain or significant erythema on the non-palmoplantar skin)
- Grade 2 (Erythema or irritation on the non-palmoplantar skin requiring intervention)
- Any AE definitely or probably related to regorafenib

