5.4 General Concomitant Medication and Supportive Care Guidelines

Concomitant use of systemic retinoids, treatment dose steroids or topical steroids for HFSR prior to the development of symptoms is prohibited. Other systemic agents for the treatment of HFSR are prohibited. Topical agents beyond that outlined as best practice standards (“BPS”) are prohibited.

Because there is a potential for interaction of Tazarotene with other concomitantly administered drugs through the cytochrome P450 system, the case report form must capture the concurrent use of all other drugs, over-the-counter medications, or alternative therapies. The Overall PI should be alerted if the participant is taking any agent known to affect or with the potential to affect selected CYP450 isoenzymes. Appendix C presents guidelines for identifying medications/substances that could potentially interact with the study agent(s).

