7.4 Reporting to the Food and Drug Administration (FDA)

The Overall PI, as study sponsor, will be responsible for all communications with the FDA. The Overall PI will report to the FDA, regardless of the site of occurrence, any serious adverse event that meets the FDA's criteria for expedited reporting following the reporting requirements and timelines set by the FDA.

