12.2 Data Safety Monitoring

The DF/HCC Data and Safety Monitoring Board (DSMB) will review and monitor study progress, toxicity, safety and other data from this study. The Board is chaired by a medical oncologist from outside of DF/HCC and its membership composed of internal and external institutional representation. Information that raises any questions about participant safety or protocol performance will be addressed by the Overall PI, statistician and study team. Should any major concerns arise, the DSMB will offer recommendations regarding whether or not to suspend the study.

The DSMB will meet twice a year to review accrual, toxicity, response and reporting information. Information

to be provided to the DSMB may include: participant accrual; treatment regimen information; adverse events and serious adverse events reported by category; summary of any deaths on study; audit results; and a summary provided by the study team. Other information (e.g. scans, laboratory values) will be provided upon request.

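### Section 7.3.4 waives expedited reporting of every AE attributed to regorafenib, with no limit on seriousness; this conflicts with 7.3.1 for life-threatening or unanticipated events and may delay reports needed under 7.4

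*Combined protocol and SAP*

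**What the plan says.** Section 7.3.4 sets out protocol-specific exclusions: events that "do not require expedited reporting to the Overall PI or the DFCI IRB", although they must still be entered on the case report form. There are three entries. Two describe irritation of non-palmoplantar skin, one at grade 1 or below and one at grade 2. The third reads "Any AE definitely or probably related to regorafenib" and carries no qualifier.

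Four neighbouring clauses bear on it:

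- **7.3.1:** "In the event of an unanticipated problem or life-threatening complications treating investigators must immediately notify the Overall PI". No exception is made for attribution.
- **7.3.2:** investigators must "report to the Overall PI any adverse event (AE) that occurs after the initial dose of study treatment", through 28 days after the last dose, on the local SAE form. No submission deadline is given.
- **7.4:** the Overall PI, as sponsor, "will be responsible for all communications with the FDA" and must report qualifying serious events on FDA timelines.
- **7.7:** all AEs go to the Overall PI in routine submissions on toxicity forms, again without a stated deadline.

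Sections 7.2 and 7.6 give a five-level attribution scale worded for relation to study treatment. Section 5 says that regorafenib is not provided by the study.

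**The concern.** Every participant takes regorafenib, so the third entry can apply to anyone in the trial, and the only condition for the waiver is the investigator's causality judgment. Read literally, a fatal or life-threatening event leaves the expedited route once it is called probably related to regorafenib.

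That judgment is hardest where the trial most needs it. The tazarotene AE list in 7.1 includes skin pain, desquamation, fissuring and bleeding. The hand-foot grading in Section 11 lists peeling, fissures and bleeding with pain. The gel goes on the palms and soles, where HFSR occurs, and the investigator is blinded. Section 5.4 also says that "there is a potential for interaction of Tazarotene with other concomitantly administered drugs through the cytochrome P450 system", so an event may belong to more than one agent.

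At stake is how promptly the Overall PI learns of a serious event. The PI holds the FDA reporting duty and, under Section 4.1, is the person who requests emergency unblinding, including for expedited safety reporting.

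**Working it through.** No arithmetic applies: the point concerns how the clauses fit together and uses no rate, sample size or error level. The check puts kinds of event through the clauses as written.

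| Event | 7.3.1 | 7.3.4, third entry | 7.3.2 and 7.7 | Result |
|---|---|---|---|---|
| Non-serious, known regorafenib toxicity | Not engaged | Expedited report waived | Reaches PI, no deadline | No conflict; a reasonable purpose for the waiver |
| Serious, not life-threatening and not unanticipated, probably due to regorafenib | Not engaged | Waived | Reaches PI, no deadline | No direct contradiction, but no prompt route |
| Life-threatening, or an unanticipated problem, probably due to regorafenib | Immediate notice required | Waived | Reaches PI, no deadline | Conflict; no rule of precedence |
| Serious, probably due to regorafenib and possibly due to the gel | Depends on the event | Waived as written | Reaches PI, no deadline | A possible gel event is exempt |

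**Does another clause supply the missing limit?** Section 7.6 has an expectedness filter: AEs of the listed agents are expedited only if they depart from the expected toxicity information. The only list in 7.1 is for tazarotene, so the filter sets no boundary for regorafenib. The first two entries of 7.3.4 and the Section 6 table describe non-palmoplantar skin only, so they do not classify a severe reaction on the palm or sole as gel toxicity.

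**Is the trigger defined?** The scale in 7.2 and 7.6 rates relation to study treatment. The third entry needs a rating against regorafenib, which the study does not supply. The same five words could be applied to it, but neither section asks for this, and no clause says how an event rated against both agents is handled.

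**What does this do to 7.4?** The PI can meet FDA timelines only for events already known to the PI. For exempt serious events outside 7.3.1, the remaining routes are 7.3.2 and 7.7, and neither sets a deadline. Section 7.4 is therefore put at risk. Whether a given regorafenib-attributed event would meet the FDA criteria cannot be settled from these documents.

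**The case against.** The best defence is that regorafenib is background treatment with well-known toxicity, and that expediting every such event would burden the PI and the IRB to little purpose. The clauses can also be read together: 7.3.1 continues to govern life-threatening and unanticipated events, and 7.3.4 trims the rest. The phrase limiting 7.3.4 to this protocol follows the general IRB reporting policy in 7.3.3 and may be meant only as a departure from that. Because 7.3.2 has no deadline, waiving expedited reporting does not plainly contradict it. Section 7.5 separately sends certain safety reports to Risk Management.

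The purpose is legitimate and the harmonised reading is possible, but the text does not state it. Nor does that reading help with serious events outside 7.3.1 or with dual attribution.

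The defence does defeat several stronger inferences:

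- *That the PI never learns of these events.* Sections 7.3.2 and 7.7 still send all AEs to the PI; only the expedited route is waived.
- *That worsening of hand-foot toxicity would go unseen.* HFSR is the primary endpoint, assessed at scheduled visits whatever its attribution. The Section 13.2 interim futility look also compares the arms on it.
- *That the number of lost reports can be found by applying the Section 2.1 grade 3 rates to the sample size.* Those are background rates for regorafenib generally, whereas this trial requires a planned dose escalation and recommends urea in both arms. The sample of 70 is a maximum, and grade 3 is not the same as serious.
- *That the waiver lengthens the wait for independent review.* Section 12.2 says "The DSMB will meet twice a year to review accrual, toxicity, response and reporting information". That schedule is the same with or without 7.3.4, which concerns the PI and the IRB.

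**Conclusion.** The point stands as a defect in the safety-reporting rules. The third entry of 7.3.4 is unlimited where the two entries beside it are limited. It conflicts with 7.3.1 for life-threatening events and unanticipated problems attributed to regorafenib, with no rule of precedence. For other serious events it leaves only undated routes to the person who owes the FDA report. It also exempts an event that may be partly due to the gel.

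A reader might infer that 7.4 is broken outright, or that investigators will systematically blame regorafenib for gel reactions. The documents show neither. They show that a late report is possible and that attribution on palms and soles is ambiguous.

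The size cannot be put in numbers from these documents. The conclusion rests on reading 7.3.4 as written, and on there being no unstated site procedure that sets deadlines for 7.3.2 or 7.7. If the institutional IRB policy cited in 7.3.3 supplies deadlines, the delay would be smaller, but the conflict with 7.3.1 and the dual-attribution gap would remain. The efficacy analysis is untouched.

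**What to change.** Reconcile 7.3.1, 7.3.2, 7.3.4 and 7.4:

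1. Limit the third entry of 7.3.4 to AEs that are non-serious, expected for regorafenib, and judged unlikely or unrelated to the gel. Name the reference used for expectedness, since 7.1 lists only tazarotene.
2. State that 7.3.1 and 7.4 take precedence, so that serious, life-threatening, fatal or unanticipated events are expedited whatever the attribution.
3. In 7.2 and 7.6, record attribution separately for the gel and for regorafenib, so that an event possibly due to both is not exempt.

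The cost is a few sentences of amendment, one added attribution field on the toxicity form, and somewhat more expedited reports of serious regorafenib toxicities that are already known. The saving on non-serious background toxicity is kept.

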7.4 Reporting to the Food and Drug Administration (FDA)

The Overall PI, as study sponsor, will be responsible for all communications with the FDA. The Overall PI will report to the FDA, regardless of the site of occurrence, any serious adverse event that meets the FDA's criteria for expedited reporting following the reporting requirements and timelines set by the FDA.

7.5 Reporting to Hospital Risk Management

Participating investigators will report to their local Risk Management office any participant safety reports, sentinel events or unanticipated problems that require reporting per institutional policy.

7.6 Adverse Event Characteristics

- **CTCAE term (AE description) and grade:** The descriptions and grading scales found in the revised NCI Common Terminology Criteria for Adverse Events (CTCAE) version 5.0 will be utilized for AE reporting. All appropriate treatment areas should have access to a copy of the CTCAE version 4.0. A copy of the CTCAE version 5.0 can be downloaded from the CTEP web site http://ctep.cancer.gov/protocolDevelopment/electronic_applications/ctc.htm.
- **For expedited reporting purposes only:**
 - AEs for the agent(s) that are listed above should be reported only if the adverse event varies in nature, intensity or frequency from the expected toxicity information which is provided.
 - Other AEs for the protocol that do not require expedited reporting are outlined in the next section (Expedited Adverse Event Reporting) under the sub-heading of Protocol-Specific Expedited Adverse Event Reporting Exclusions.
- **Attribution of the AE:**
 - Definite – The AE is *clearly related* to the study treatment.
 - Probable – The AE is *likely related* to the study treatment.
 - Possible – The AE *may be related* to the study treatment.
 - Unlikely – The AE is *doubtfully related* to the study treatment.
 - Unrelated – The AE is *clearly NOT related* to the study treatment.

7.7 Routine Adverse Event Reporting

All Adverse Events **must** be reported in routine study data submissions to the Overall PI on the toxicity case report forms. AEs will not be reported to the drug manufacturer. **AEs reported through expedited processes (e.g., reported to the IRB, FDA, etc.) must also be reported in routine study data submissions. AEs should be reported using the CTCAE v. 5.**

8. PHARMACEUTICAL INFORMATION

A list of the adverse events and potential risks associated with the investigational administered in this study can be found in Section 7.1.

8.1 Tazarotene

8.1.1 Description

Tazarotene is a member of the acetylenic class of retinoids and its chemical name is: Ethyl 6-[2-(4,4-dimethylthiochroman-6-yl) ethynyl] nicotinate. The molecular weight is 351.46.

Following topical application, tazarotene rapidly undergoes esterase hydrolysis to form its active metabolite, tazarotenic acid. Tazarotenic acid is highly bound to plasma proteins (>99%) and little

parent compound is found after topical application and esterification. Tazarotene and tazarotenic acid are metabolized to sulfoxides, sulfones and other polar metabolites which are eliminated through urinary and fecal pathways. The half-life of tazarotenic acid is approximately 18 hours.

8.1.2 Form

Tazarotene 0.1% gel is available in a collapsible aluminum tube with a tamper-evident aluminum membrane over the opening and a white polypropylene screw cap, in 15g and 30g sizes.

8.1.3 Storage and Stability

Store at 25 degrees C (77 degrees F), with excursions permitted between -5 and +30 degrees C (23 and 86 degrees F)

8.1.4 Compatibility

N/A

8.1.5 Handling

If a person other than the patient is applying the gel, gloves should be worn or hands washed following application.

8.1.6 Availability

Tazarotene 0.1% gel is available from various manufacturers and will be distributed by research pharmacy. Bayer will provide funding to cover the cost of the Tazarotene.

8.1.7 Preparation

A 30 gram tube will be supplied to the patient monthly (every 4 weeks). For participants with larger hands and feet, it is permissible to dispense two 30 gm tubes of Tazarotene 1% gel/Placebo. Earlier visits for dispensing are allowed if participants run out of drug early. Please refer to Appendix E: Tazarotene or Placebo Preparation Instructions

8.1.8 Administration

$\frac{1}{2}$ Finger tip unit will be applied per palm/sole (1FTU=2% BSA). 1gram of gel covers 4% BSA. 1 palm is 1%, therefore patients will be treated with 30g per 28 day period.

One finger tip unit (FTU) is defined as the quantity of medication dispensed from a 5mm standard nozzle from the palmar side distal index finger crease to the tip.

8.1.9 Ordering

The agent is commercially available and will be ordered to ensure sufficient stock before protocol activation.

8.1.10 Accountability

The investigator, or a responsible party designated by the investigator, should maintain a careful record of the inventory and disposition of the agent using the NCI Drug Accountability Record Form (DARF) or another comparable drug accountability form. (See the NCI Investigator's Handbook for Procedures for Drug Accountability and Storage.)

8.1.11 Destruction and Return

Unused supply of tazarotene will be returned to pharmacy and weighed for drug accountability at the 4-week, 8 week and 12 week study visits.

8.2 Placebo

8.2.1 Description

Clear Wave Ultrasound Gel will be used as the placebo in this study as it closely matches the color and consistency of the active Tazarotene and is alcohol-free.

8.2.2 Form

Clear Wave Ultrasound Gel is available in 8oz tubes

8.2.3 Storage and Stability

Store at controlled room temperature

8.2.4 Compatibility

N/A

8.2.5 Handling

If a person other than the patient is applying the gel, gloves should be worn or hands washed following

application.

8.2.6 Availability

Clear Wave Ultrasound Gel is available in 8oz tubes and will be paid for by the study cost center

8.2.7 Preparation

A 30-gram tube will be supplied to the patient monthly (every 4 weeks). For participants with larger hands and feet, it is permissible to dispense two 30 gm tubes of Tazarotene 1% gel/Placebo. Earlier visits for dispensing are allowed if participants run out of drug early. Please refer to Appendix E: Tazarotene or Placebo Preparation Instructions for study drug preparation.

8.2.8 Administration

One half finger tip unit will be applied per palm/sole (1FTU=2% BSA). 1-gram gel covers 4% BSA. 1palm is 1%, therefore patients will be treated with 30gm per 28-day period.

One finger tip unit (FTU) is defined as the quantity dispensed from a 5mm standard nozzle from the palmar side distal index finger crease to the tip.

8.2.9 Ordering

Clear Wave Ultrasound Gel is commercially available and will be ordered to ensure sufficient stock and paid for by the study cost center.

8.2.10 Accountability

The investigator, or a responsible party designated by the investigator, should maintain a careful record of the inventory and the disposition of the agent using the NCI Drug Accountability Record Form (DARF) or another comparable drug accountability form. (See the NCI Investigator's Handbook for Procedures for Drug Accountability and Storage)

8.2.11 Destruction and Return

Unused supply of tazarotene or placebo will be returned to pharmacy and weighed for drug accountability at the 4-week, 8 week, and 12-week study visits.

9. BIOMARKER, CORRELATIVE, AND SPECIAL STUDIES

Correlative studies are optional.

Patients will be asked if they would like to participate until 16 patients are identified.

- Day 1 and 4-week (+/- 2 weeks) skin biopsies will be obtained and processed in formalin fixed, paraffin embedded blocks. The pre-biopsy will be obtained from the non-dominant lateral palm. The 4-week biopsy will be obtained from the same area or an area of HFSR, if present.
- A 4mm punch biopsy will be obtained from up to 16 patients (up to 6 will be analyzed in each study arm); we suspect that half of patients in the control arm will develop HFSR on regorafenib and half will not. This will allow for comparison across arms and between affected and non-affected individuals to look for a signal of difference.

Biopsies will be analyzed using standard immunohistochemistry and cyclic immunofluorescence, for the presence of activation of transcription factors known to be associated with hyper-proliferative inflammatory acquired and genetic skin disorders.

Additionally, RNA transcriptional profiling will be performed to compare those patients who develop HFSR from those who do not use the Nanostring platform on formalin-fixed, paraffin embedded tissue. Gene sets previously developed for inflammatory skin disorders will be used.

Skin biopsy specimen collection and shipment will be paid for by Bayer Pharmaceuticals.

Left over specimens will be banked for future use.

The study team will have access to banked specimens.

9.1 Biomarker Studies

N/A

9.2 Laboratory Correlative Studies

9.2.1 Optional Correlative Skin Biopsies #1

Collection of Specimen(s): 4 mm skin punch biopsy. Skin biopsy will be placed in formalin at time of collection.

Handling of Specimens(s): Skin biopsy will be sent to the pathology core on the same day of collection to be made into a FFPE block.

Specialized Histopathology Core

Brigham and Women's Hospital

[name]

[name]

FFPE blocks will be stored in the PI's office at [name] until all patient FFPE blocks have been obtained. At that time, they will be sent in a batch to be cut into slides.

9.2.1.3 Shipping of Specimen(s): Slides will be couriered over to the [name] Lab for analysis once all patient biopsies have been obtained.

9.2.1.4 Site(s) Performing Correlative Study:

[name] Lab

[name]. Harvard Medical School

[name]

[name]

[name]

[contact]

[contact]

Administrative Coordinator:

[name]

[contact]

[name]

10. STUDY CALENDAR

Baseline evaluations are to be conducted within 1 month prior to start of protocol therapy. Assessments must be performed prior to administration of any study agent. Study assessments and agents should be administered within \pm 3 days of the protocol-specified date, unless otherwise noted.

	Pre-Study	Cycle 1			Cycle 2		Cycle 3	Cycle 4	Cycle 5	Cycle 6	Off Study ^f
		Day 1 (Wk 0)	Day 15 (Wk 2)	Day 28 (Wk 4)	Day 42 (Wk 6)	Day 56 (Wk 8)	Day 84 (Wk 12)	Day 112 (Wk 16)	Day 140 (Wk 20)	Day 168 (Wk 24)	
		-28 days		+/-3 days	+/-3 days	+/-3 days	+/-3 days	+/-7 days	+/-7 days	+/-7 days	28 days +/- 7
First dose of Regorafenib		X									
First dose of Tazarotene		X (no more than +/- 96 hours from first Regorafenib dose)									
Study Drug Dispensation: Tazarotene or placebo^a	X			X		X	X	X	X	X	
Study Drug Accountability: Tazarotene or placebo				X		X	X				
Informed consent	X										
Demographics	X										
Medical history	X										
Concurrent meds	X	X-----X									
Physical exam	X		X	X	X	X	X	X	X	X	
Performance status	X										X
Questionnaires: HFS-14, Epidemiology Questionnaire, DLQI, Skindex16, Perceived Stress Scale Assessments ^b	X		X	X	X	X	X	X	X	X	
Adverse event evaluation		X-----X									X
B-HCG ^c	X										
Other optional correlative skin biopsies ^d	X			X (+/- 2 wk)							
ODO Randomization^e	X										

a: Tazarotene or placebo dispensation. Tazarotene will be dispensed at the pre-study visit. Tazarotene dosing starts on Day 1 along with the first dose of regorafenib. Day 1 regorafenib and tazarotene/placebo dosing could possibly occur on the same day as the pre-study visit, after the patient has been registered and randomized; this would not be considered a protocol deviation. The starting dose of regorafenib is what is considered Day 1 and all other timepoints are based on that. There is no required order for the Day 1 regorafenib and tazarotene/placebo doses. It is preferred that the patients begin their tazarotene/placebo dose on the same day as their start of regorafenib dose (on Day 1). If however for whatever reason patients begin their tazarotene/placebo dose +/- 96 hours (4 days) from their first regorafenib dose, this will not be considered a protocol deviation, but will be noted in the data.
 
b: Epidemiology questionnaire should be completed once at screening. All other questionnaires should be collected at the indicated timepoints. These may be collected in either paper or electronic formats.
 
c: Serum pregnancy test (women of childbearing potential ONLY).
 
d: Optional skin biopsies will be obtained from a cohort of 6 patients in each arm (first 6 patients in each arm that consent to these optional biopsies)
 
e: Randomization occurs after all screening assessments have been completed and the patient's eligibility has been confirmed. This could be the same day as the screening visit or anytime up to and including Day 1. ODO will send the randomization to the research pharmacy.
 
f: Off-study treatment evaluation. This will occur 28 days +/- 7 days after the last regorafenib and tazarotene/placebo.
											

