5.5 Criteria for Taking a Participant Off Protocol Therapy

Duration of therapy will depend on individual response, evidence of HFSR development, progression and tolerance of tazarotene. In the absence of treatment delays due to adverse event(s), treatment may continue for up to 24 weeks or until one of the following criteria applies:

- HFSR grade >/=2 develops and fails to respond to supportive interventions at the treating physician discretion
- Intercurrent illness that prevents further administration of treatment
- Unacceptable adverse event(s)
- Participant demonstrates an inability or unwillingness to comply with the topical medication regimen

and/or documentation requirements

- Participant decides to withdraw from the protocol therapy
- General or specific changes in the participant's condition render the participant unacceptable for further treatment in the judgment of the treating investigator

Participants will be removed from the protocol therapy when any of these criteria apply. The reason for removal from protocol therapy, and the date the participant was removed, must be documented in the case report form (CRF). Alternative care options will be discussed with the participant.

When a participant is removed from protocol therapy and/or is off the study, the relevant Off-Treatment/Off-Study information will be updated in OnCore.

Participants may be removed from the protocol therapy, but remain on study for the duration of the follow up period.

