5.6 Duration of Follow Up

Participants will be followed for a minimum of 28 days (4 weeks) after removal from protocol therapy or until death, or regorafenib discontinuation with resolution of HFSR, whichever occurs first. Participants who do not develop HFSR who discontinue regorafenib do not require follow up after removal from protocol therapy. Participants removed from protocol therapy for unacceptable adverse event(s) will be followed until resolution or stabilization of the adverse event. Once removed from protocol therapy, study assessments (PE, vitals, questionnaires) will take place at visits paired with medical oncology SOC visit schedule.

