14. PUBLICATION PLAN

The results of this study will be made public within 24 months of reaching the end of the study follow up period, 24 weeks after the last patient initiates therapy.

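### Sections 5.6, 7.3.2 and Study Calendar footnote f contradict each other on post-treatment adverse event follow-up, and the 5.6 waiver depends on the efficacy outcome

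*Combined protocol and SAP*

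**What the plan says.** Three rules govern what happens to an individual patient after treatment.

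- **Section 7.3.2** has investigators report "any adverse event (AE) that occurs after the initial dose of study treatment, during treatment, or within 28 days of the last dose of treatment". It has no exemption by HFSR status. Since the sentence opens with study treatment, I read the last dose as the last dose of gel.
- **Section 10, Study Calendar and footnote f.** The calendar marks an AE evaluation in the off-study column, and footnote f times that visit: "This will occur 28 days +/- 7 days after the last regorafenib and tazarotene/placebo". There is no exemption here either.
- **Section 5.6** starts from a general rule, "Participants will be followed for a minimum of 28 days (4 weeks) after removal from protocol therapy or until death", with a further early end on "regorafenib discontinuation with resolution of HFSR, whichever occurs first". It then adds a waiver: "Participants who do not develop HFSR who discontinue regorafenib do not require follow up after removal from protocol therapy". Participants removed for unacceptable AEs are followed until these resolve or stabilize. The assessments it lists after removal are physical exam, vitals and questionnaires; AE evaluation is not named.

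Three other sections bear on the point. Under section 5.5, gel "treatment may continue for up to 24 weeks or until one of the following criteria applies", while regorafenib is managed by the oncology team and may go on longer. Section 13.6.1 says when toxicity evaluation starts but not when it ends. Section 14 places the end of study follow-up at "24 weeks after the last patient initiates therapy".

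**The concern.** All three patient-level rules use 28 days, but they differ in the starting point and in who is exempt. Two kinds of patient fall between them.

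The first is HFSR-free and stops regorafenib. Section 7.3.2 and the calendar call for AE data to about day 28; section 5.6 requires no follow-up at all. Section 7.3.2 obliges the investigator to report an event but schedules no contact at which to learn of it.

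The second completes 24 weeks of gel and stays on regorafenib. The only scheduled post-treatment AE evaluation is then tied to the last regorafenib dose, a date with no upper limit, and not to the end of the gel.

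The first case matters more. Grade 2 or higher HFSR is the primary endpoint and HFSR of any grade is a secondary one. A waiver conditioned on HFSR makes the length of safety observation depend on the outcome that the gel is meant to change. If the gel works, late-onset AEs could be looked for less often in the tazarotene arm, and the toxicity summary in 13.6.1 would compare arms observed for different lengths of time.

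**Working it through.** **1. Inputs.** Section 13.2 gives all-grade HFSR of 55% with placebo and 30% with tazarotene, 35 patients per arm, a one-sided 10% test and 82% power. The documents do not give the share of HFSR-free patients who discontinue regorafenib. I call it d and vary it from 0.25 to 1.00 (assumption). I also take the section 13.2 rates as the share with HFSR by the time regorafenib stops (assumption).

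**2. The plan's own figure.** With a pooled variance under the null, power = Phi[(0.25 x sqrt(35) - 1.2816 x sqrt(2 x 0.425 x 0.575)) / sqrt(0.55 x 0.45 + 0.30 x 0.70)] = Phi[(1.479 - 0.896) / 0.676] = 0.806. With an unpooled variance it is 0.817. Both agree with 82% to within 2 points, so the rates are read correctly.

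**3. Share waived.** Waived share = (1 - HFSR rate) x d. HFSR-free shares are 1 - 0.55 = 0.45 and 1 - 0.30 = 0.70, a ratio of 1.56. Patients waived, with d equal in both arms:

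| d | Placebo, of 35 | Tazarotene, of 35 | Gap (points) |
|---|---|---|---|
| 0.25 | 3.9 | 6.1 | 6.3 |
| 0.50 | 7.9 | 12.3 | 12.5 |
| 0.75 | 11.8 | 18.4 | 18.8 |
| 1.00 | 15.8 | 24.5 | 25.0 |

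If 7.3.2 or footnote f is applied to everyone, the waived share is 0 in both arms. It is also equal in both arms if the gel has no effect and d is the same.

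**4. How firm the direction is.** The gap is zero when d with tazarotene is 0.45 / 0.70 = 0.64 times d with placebo, and reverses below that. With d = 0.75 on placebo and 0.40 on tazarotene, 11.8 placebo and 9.8 tazarotene patients are waived.

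**5. The other early end in 5.6.** Follow-up can also stop for patients with HFSR who discontinue regorafenib and resolve. If a fraction r resolve within the window, the share ending early = d x [(1 - p) + p x r], where p is the HFSR rate. At d = 0.50:

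- r = 0: 22.5% placebo, 35.0% tazarotene
- r = 0.5: 36.3% and 42.5%
- r = 1: 50% and 50%

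**6. Effect on total observation.** Share of AE time kept = (T + 28 x (1 - waived share)) / (T + 28), with T days on treatment. The gap between arms is 28 x 0.25 x d / (T + 28). For T = 56 it is 2.1 to 8.3 points; for T = 168 it is 0.9 to 3.6 points.

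**7. Events at stake.** Suppose 10% of patients have an event that starts in the 28-day tail and none is captured in waived patients (both assumptions). At d = 0.50, 35 x 0.10 x 0.225 = 0.79 placebo and 35 x 0.10 x 0.35 = 1.22 tazarotene patients would be missed. With tail rates of 5% to 20% and d of 0.50 to 1.00, the range is 0.39 v 0.61 up to 3.15 v 4.90.

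**The case against.** The strongest reply is that AE collection is never clearly waived. Section 7.3.2 is the only passage that defines an AE reporting window, and it covers everyone; section 7.7 requires all AEs on the case report forms; 5.6 concerns follow-up and does not mention AE collection. That stands against any claim that AE data will be absent. It does not remove the contradiction, because a site that follows 5.6 has no planned contact at which to ask.

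The reply also limits the harm, and most of it stands. Section 13.6.1 is descriptive and counts events that are new or worsening from first dose, so a reaction that starts on gel and persists is already counted. Unacceptable AEs leading to removal are followed to resolution or stabilization. The tolerability summary in section 13.2 concerns events that require stopping study therapy, which the waiver cannot touch. The listed gel reactions are mainly local, and section 8.1.1 gives the active metabolite a half-life of about 18 hours, so the documents give little reason to expect many late-onset gel events.

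A reader might infer four different ends to AE collection by counting section 14. The text does not support that: section 14 names an end of follow-up only to start a publication clock and stops no AE collection. A reader might also infer that the 24-week completer still on regorafenib gets no follow-up. That patient is not waived, because 5.6 calls for at least 28 days after removal from protocol therapy, although it does not say whether completing 24 weeks counts as removal.

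**Conclusion.** The contradiction between 5.6, 7.3.2 and footnote f is in the text and should be resolved. Applying 5.6 as written could make ascertainment of late-onset AEs differ by arm: at the plan's all-grade rates and equal discontinuation of 25-100%, 6 to 25 percentage points more tazarotene than placebo patients (2.2 to 8.8 of 35) would be waived.

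It is tempting to go further and conclude that AEs will be under-counted in the tazarotene arm. The documents do not support that. The waiver needs two conditions, HFSR-free status and regorafenib discontinuation, and the second has no rate in the plan. Section 2.1 names HFSR as a leading reason for changing or stopping regorafenib, so discontinuation is unlikely to be independent of HFSR. The 30% is a power alternative, not a forecast. The gap also narrows as HFSR resolves early under 5.6, and vanishes or reverses once discontinuation among HFSR-free tazarotene patients falls to 0.64 times the placebo rate or lower.

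Only events that begin or worsen after the last application are exposed. On-treatment AEs, unacceptable AEs leading to removal, and every power, alpha and sample-size figure are unaffected.

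**What to change.** Reconcile 5.6, 7.3.2 and footnote f to one AE window with one anchor that does not depend on HFSR status. One workable form is an AE contact, by phone if convenient, 28 +/- 7 days after the last gel application for every treated participant, whatever the HFSR or regorafenib status. Then:

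- limit the 5.6 waiver to in-person assessments, and say whether completing 24 weeks of gel counts as removal from protocol therapy;
- state the end of the toxicity window in 13.6.1;
- align section 14's end of follow-up with that window. For a last-enrolled patient treated for the full 24 weeks, 168 + 28 = 196 days is week 28, or 203 days (week 29) at the end of the visit allowance.

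The cost is wording in five places and one phone contact for each patient now waived. Aligning section 14 moves the stated end of follow-up by about 4 to 5 weeks. Nothing in the efficacy design changes.
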